## **Study Protocol**

**STUDY TITLE:** BRIDGE Device for Symptoms of Opioid Withdrawal: A Randomized, Double-Blind, Placebo-Controlled Study.

#### **STUDY PURPOSE**

A recent retrospective study demonstrated evidence for the rapid and effective attenuation of signs and symptoms associated with opioid withdrawal using the BRIDGE device (Innovative Health Solutions, Versailles, IN, USA). While there was no control group in that study, it did show a high degree of success in treating withdrawal symptoms and transitioning patients (88%) to long-acting naltrexone (XR-NTX) (1). The BRIDGE device is a novel, non-pharmacological, non-invasive, auricular percutaneous electrical nerve field stimulator (PENFS) that is thought to significantly reduce pain and modulate the autonomic nervous system. The novelty of this device is in the use of alternating current and higher voltage stimulation over a large field in the external ear that allows access into central brain regions involved in fear and pain modulation. The purpose of the study is to prospectively evaluate the effectiveness this new, FDA-cleared device in reducing signs and symptoms of acute, opioid withdrawal compared to placebo. This will be tested with the following specific aims:

#### **SPECIFIC AIMS/HYPOTHESIS**

Aim 1: Determine the severity of opioid withdrawal symptoms in patients using the BRIDGE device versus sham (inactive device) during active withdrawal in a double-blind, randomized controlled study design. Hypothesis: Treatment with the BRIDGE device will have a significant and profound effect on decreasing opioid withdrawal scores compared to sham.

**Aim 2:** Assess improvements in pain, craving and cognition in patients using the BRIDGE device versus sham (inactive) device. **Hypothesis**: Neuromodulation with the BRIDGE device will have a significant and profound effect on decreasing pain and craving scores quickly in the two hours following application as well as the ensuing 4-5 days. It will also demonstrate improvement in memory and executive function compared to sham treatment.

#### **BACKGROUND AND RATIONALE**

Results of a retrospective study in adults going through opioid withdrawals suggest that the BRIDGE device can decrease symptoms of opioid withdrawal by over 87% within the first hour of treatment without the use of supportive medication. Pre-clinical studies in rats suggest that neurostimulation with the BRIDGE decreases neuronal activity in the central amygdala (2). The amygdala is a common central link between a state of chronic pain and opioid dependence. As this central nervous system structure is involved in pain processing activation it has been associated with fear and the negative emotional state of withdrawal from opioids and drug craving (3-5). It is therefore likely that the BRIDGE device will impact pain and symptoms associated with opioid withdrawal. It is well known that there is a high prevalence of pain in persons with OUD during acute opioid withdrawal. A recent study concluded that in many cases, pain is a major reason for patients opting out of treatment (6). Another study demonstrated that up to 37.5 % of patients drop out of therapy within the first month and the majority of those occur during the first week (7.8). Early dropout is often the result of severe and dysphoric symptoms of withdrawal. Thus, alleviating signs and symptoms of withdrawal effectively and rapidly at the initial time of engagement is likely to increase the likelihood of success of any treatment protocol. The first few hours and days of therapy are critical to get patients engaged thus willing to enter into secondary therapy with pharmacotherapy and counseling to prevent relapse. In a recent study, 29% of patients who were randomized to receive MAT with opioid antagonists dropped out of treatment and did not receive the first dose of medication (9).

Overall, it is well known that pharmacotherapy used to treat patients during withdrawal usually falls short of completely alleviating symptoms rapidly and effectively (10,11). While it is accepted that opioid agonists such as buprenorphine relieve symptoms of opioid withdrawal, the literature suggests that this reduction is not, by any means, complete or rapid. Gunderson et.al. studied 758 opioid dependent subjects in a prospective, randomized, multicenter trial (12). Subjects used either higher bioavailability formulation of buprenorphine/naloxone or generic as induction agent. COWS scores were measured at several time points (**Figure 1A**). An approximate average score of 7.5 was seen in both groups by the first hour with an average starting COWS score of 15, suggesting a 50% decrease in withdrawal symptoms. Interestingly, patients were allowed rescue medication if needed, but no specific data were given regarding supportive care. While improvement in opioid craving decrease (Figure 1B) (13). Increased craving and withdrawal symptoms have been identified as negative predictors for favorable treatment outcomes in patients with substance use disorder. Therefore, improvement in craving with the BRIDGE device in patients treated with buprenorphine during the first week of therapy could significantly impact treatment outcomes and/or patient comfort.

**Figure 1.** A) Mean time profile of total scores on the clinical opiate withdrawal scale (COWS) with buprenorphine/naloxone. B) Weekly craving and withdrawal scores after induction with buprenorphine. Craving scores do not significantly decrease until after the first week of treatment. Figure shows a subsequent increase in craving and withdrawal after tapering the doses of buprenorphine at week 2.

A separate study showing effects of buprenorphine/naloxone showed very similar results (14). That study examined buprenorphine/naloxone induction of 69 participants who self-reported primary PO use of methadone, ER-oxycodone, IR-oxycodone, or hydrocodone. COWS scores were measured one hour after the initial dose of medication. The percent decreases in COWS scores in the first hour ranged from 53-58%. (Table 1).

	ER oxycodone	IR oxycodone	Methadone	Hydrocodone
Participant characteristics	n = 219	n = 107	n = 41	n = 202
Induction outcomes				
Mean pre-dose COWS Score	12.7 (SD 3.5)	12.4 (SD 3.5)	13.0 (SD 3.6)	12.7 (SD 3.5)
Mean post-dose COWS Score	5.3 (SD 3.9)	5.8 (SD 3.9)	5.6 (SD 4.8)	5.9 (SD 4.1)

In contrast, the recently published retrospective study with the BRIDGE device resulted in an 87% reduction in opioid withdrawal symptoms within the first hour of treatment without the use of supportive medications and a 97% reduction by day 5 (1) (**Figure 2**). Although the benefits of the BRIDGE device in alleviating symptoms of

withdrawal were striking in this retrospective assessment, the placebo effect cannot be ignored. Therefore, it is important to evaluate the potential benefits of neurostimulation in patients suffering from symptoms of opioid withdrawal as they may impact patient comfort, retention in treatment, and types and doses of medication used.

#### Figure 2

The clinical opiate withdrawal scale (COWS) is commonly used in drug treatment protocols to assess the severity of acute withdrawal (15,16). This tool limits the possibility of feigned responses by combining subjective symptoms (GI upset, anxiety, irritability, muscle aches, nausea, restlessness, craving, chilling) with objective signs (heart rate, sweating, restlessness, pupil size, runny nose, tremors, yawning, and piloerection). Common pharmacotherapies use medications which have strong affinity for opioid receptors and gradually displace opioids from binding sites. This makes withdrawal symptoms inevitable. Other approaches such as electroacupuncture have been suggested to improve symptoms related to opioid withdrawal. Unfortunately, studies show that these techniques can have a delay of up to 2 days in demonstrating efficacy, even with the concomitant use of opioid receptor agonists (17). A delay in efficacy of any treatment in this population at the initial time of engagement is extremely undesirable.

#### **DESIGN AND METHODS**

The study will recruit a total of 50 subjects and will take place in a well-established outpatient treatment center (Brightview). Brightview is a private addiction treatment center located in Cincinnati, Ohio. The site PI at Brightview will be [name] [name] (MD, ABIM, ABAM DABPM), a board-certified physician in addiction medicine. [name] (PhD) will be a Co-investigator. The volume of patients treated for opioid use disorder (OUD) at this facility is sufficient for patient recruitment in this study. [name] will be responsible for patient recruitment and overseeing the entire project at Brightview. He will monitor the health of all patients in the study per standard clinical practice. [name] will be responsible for patient recruitment as well and monitor protocol adherence as well as supervise data collection, entry, and analysis.

This study will involve a double-blind, randomized, controlled trial with active BRIDGE or sham device (Figure 3). The sham device will be identical in appearance to the active device but will have no electrical current. Both providers and patients will be blinded to treatment allocation throughout the study. Participants will be 18 years or older who speak English and meet criteria for opioid use disorder based on the Diagnostic and Statistical Manual of Mental Disorders-5. Patients going through acute opioid withdrawal will be assessed for the severity of opioid withdrawal using the Clinical Opioid Withdrawal Scale (COWS). Additional demographic data will be collected at presentation including age, sex, duration of opioid misuse, types of medications or illicit drugs used as well as the presence of other medical conditions. After the severity of opioid withdrawal is established (COWS score  $\geq 10$ ), subjects will be randomized in blinded fashion. Once the patient is consented, a visual analog scale (VAS) for pain and an opioid craving scale (OCS) will be completed. Baseline cognitive function will be measured with the Stroop test using the CNS Vital Signs (CNSVS) in-office neurocognitive testing software https://www.cnsvs.com/index.html. This instrument measures executive function. The test takes approximately

4 minutes to administer and will be performed at the same intervals as COWS score, pain and craving assessments before and after device placement.

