#### DATA MANAGEMENT

Subjects will be randomized in a 1:1 ratio to receive either active or a sham device. Randomization in blocks of 10 (5 for each treatment) will be determined using the computer program randomization.

The severity of opioid withdrawal signs and symptoms will be assessed with the COWS at several time points: 1) pre-device placement, 2) 1-hour post placement of sham or active device, 3) two hours post placement (approximately one hour after first dose of buprenorphine), 4) at subsequent follow-up in clinic on day 2 and 5) at final follow-up in clinic on day 5 prior to removal of device. The visual analogue pain and craving scale will also be administered at intervals to monitor patient comfort: 1) pre-device placement, 2) 1-hour post placement of sham or active device, 3) two hours post placement (approximately one hour after first dose of buprenorphine),4) at subsequent follow-up in clinic on day 2, 5) in clinic or remotely (via phone) on days 3 and 4, and 6) at final follow-up in clinic on day 5 prior to removal of device. Assessment of cognitive function (CNSVS) will be recorded at 1) pre-device placement, 2) 1-hour post placement of sham or active device, and 5) at final follow-up in clinic on day 5 prior to removal of device. One hour following placement of either sham or active device, the patients will be given the first dose of buprenorphine with a starting dose of 2, 4 or 8 mg at the blinded provider's discretion based on BMI, patient previous experience with BUP, patient apprehension or other factors. Adjustments to this dose will not be made for at least an hour after receiving the first dose but the providing clinician may order additional buprenorphine after one hour as indicated by initial response, previous experience, presence of precipitated clinical opioid withdrawal scale (COWS) and BMI. Subsequent adjustments will be made based on the blinded provider's discretion and patient needs and comfort as per clinic standard. Ancillary (supportive) medications to help manage signs and symptoms of opioid withdrawal will NOT be allowed for one hour after the first dose of buprenorphine. Following the first hour, symptom control medications including ibuprofen, clonidine, ondansetron, loperamide, and acetaminophen may be furnished or prescribed. A medication log will be provided to track usage of this modality. Subjects will remain blinded and keep the device on for 5 days regardless of randomization status. Subjects will be asked to return to clinic for additional induction visits based on the clinic standard of care which will be Day 2 and in some cases Days 3 & 4. In order to monitor whether neurostimulation with the BRIDGE has any added benefit for patients on outpatient opioid agonist therapy, subjects (regardless of active or placebo) will be reassessed using OCS and VAS at each subsequent visit, or remotely (via phone) when unrequired to return to clinic, during the 5-day trial.

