#### Power Calculation for primary aim (difference in COWS scores between active and sham device).

We hypothesize that compared to sham treatment, the improvement in COWS due to the BRIDGE device will be significantly higher than the sham. Similarly, pain and craving as measured by the VAS and OCS will be reduced. Patients with the active BRIDGE device will have improved memory and executive function compared to sham as assessed by CNSVS.

The primary outcome is comparison of change from baseline of the COWS scores between active and sham device at one hour. The data will be analyzed as a randomized, placebo-controlled trial with an interim analysis when 24 patients are completed at a P< 0.001. We will compare the bridge device and sham using a two sided t-test of the change of COWS at one hour form baseline. Using the sample size software Pass 15 with 25 subjects in each group we will have at least 90% power at an alpha of 0.049 to detect a difference in the COWS at one hour between treatment and sham of at least .94 standard deviations(SD), In the withdrawal study we had a SD of ~6, and so if we have a similar variability we will be able to detect a difference of approximately 5.7 (1). In the paper, we found a difference of > 12, so even allowing for a placebo effect we should have adequate power.

Period	Baseline	(1-hour after BRIDGE)	(1-hour after BUP)	Post- MAT	Post- MAT	Post- MAT	Post- MAT
Contact	Clinic	Clinic	Clinic	Phone	Phone	Phone	Clinic
Project Day	1	1	1	2	3	4	5
Informed Consent	Х						
Demographics and Medical History	Х						
Prior and Concomitant Medications	Х						х
Vital Signs, height, weight and BMI	х						
Physical Examination	Х						
Placement of BRIDGE Device or sham	Х						
COWS scores	Х	х	Х	х			х
VAS pain and craving scale	Х	х	Х	Х	х	Х	Х
Neurocognitive assessment	Х	x					Х
First dose of Buprenorphine		Х					

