#### **Demographic Information**

Data will be collected as part of the clinic visit. This includes subject's date of birth, age, sex and ethnicity. The physician assessment will also include questions about prior medical diagnoses, co-morbid symptoms and the characteristics of the current illness. Types of illicit drugs used other than opioids (benzos, alcohol, etc.), duration of drug use, underlying psychiatric disorders.

Efficacy Information

- 1. Clinical Opioid Withdrawal Scale (COWS) (total time 5 min)
- 2. Pain (11-point VAS) (total time 2 min)
- 3. Opioid Craving Scale (11-point scale) (total time 3 min)

a. How much do you currently crave opiates (Range: 0-10, 0 = not at all, 10 = extremely)

b. In the past week, please rate how strong your desire to use opiates has been when something in the environment has reminded you of opiates (examples: seeing a medication bottle, using the Internet, visiting a doctor's office, going to a place where you used to buy drugs)? (Range: 0-10, 0 = not at all, 10 = extremely)

c. Please imagine yourself in the environment in which you previously used opiates (examples: a party, a hangout, a particular room where you live). If you were in this environment today and if it were the time

of day that you typically used opiates, what is the likelihood that you would use opiates today? (Range: 0-10, 0 = not at all, 10 = extremely)

- 4. CNS Vital Signs in-office neurocognitive testing with domain scores (total time 15 min). https://www.cnsvs.com/index.html
- 5. Four question patient questionnaires at end of study period
- 6. Dosing of medication assisted therapy (buprenorphine)
- 7. Additional (symptom control) medication log
- 8. Number of subjects with continued engagement in recovery treatment at 5 days post-device placement
- 9. Whether the patient thinks they had an active or inactive device at end of 5 days treatment

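### The cognitive test is described in two incompatible ways, and no score is named for the memory hypothesis

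*Combined protocol and SAP*

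**What the plan says.** All references are to the combined protocol and SAP.

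- **Hypothesis.** Under Specific Aims/Hypothesis, Aim 2 is to "Assess improvements in pain, craving and cognition in patients using the BRIDGE device versus sham (inactive) device". Its hypothesis adds: "It will also demonstrate improvement in memory and executive function compared to sham treatment". The Power Calculation section repeats both domains and ties them to the software: "Patients with the active BRIDGE device will have improved memory and executive function compared to sham as assessed by CNSVS".
- **Test, first description.** Design and Methods states: "Baseline cognitive function will be measured with the Stroop test using the CNS Vital Signs (CNSVS) in-office neurocognitive testing software". It continues "This instrument measures executive function", gives an administration time of about 4 minutes, and says the test "will be performed at the same intervals as COWS score, pain and craving assessments".
- **Test, second description.** Item 4 of the efficacy list under Demographic Information reads "CNS Vital Signs in-office neurocognitive testing with domain scores (total time 15 min", with no domain named.
- **Timing.** The Data Management section that sets out the assessment times says "Assessment of cognitive function (CNSVS) will be recorded at 1) pre-device placement", then at 1 hour and on Day 5. The schedule table below the power calculation marks the same three occasions.
- **Analysis.** Secondary efficacy analysis puts CNSVS into the MMRM alongside COWS, pain and craving, without saying which score. Efficacy Analysis tabulates CNSVS assessments, again without naming a score.

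**The concern.** A stated hypothesis needs a measurement that can test it and a named outcome for the analysis. For memory, the plan secures neither.

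The section that tells staff what to administer names a single test and assigns it to executive function. A coordinator who follows it to the letter collects nothing on memory, and data not collected at baseline, 1 hour and Day 5 cannot be recovered later. A coordinator who follows the efficacy list runs a longer assessment that yields several domain scores. The analyst then has to choose which of them is the CNSVS outcome, possibly after seeing the data, and no multiplicity rule is stated for secondary outcomes.

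**Working it through.** **The plan's own figure.** The only power statement concerns the 1-hour COWS change: 25 per group, two-sided alpha 0.049, a difference of 0.94 SD, at least 90% power. A two-sample t-test with the noncentral t distribution gives 90.1%, so the figure reproduces. It does not bear on cognition, for which no power is given.

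**The descriptions side by side.**

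| Section | Test | Minutes | Domain | Times |
|---|---|---|---|---|
| Design and Methods | Stroop in CNSVS software | about 4 | executive function | as COWS, pain and craving |
| Data Management | CNSVS, content not given | not given | not given | baseline, 1 h, Day 5 |
| Schedule table | neurocognitive assessment | not given | not given | baseline, 1 h, Day 5 |
| Efficacy list, item 4 | CNSVS with domain scores | 15 | plural, not named | not given |
| Secondary efficacy analysis | CNSVS | not given | not given | by visit in the MMRM |

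**Duration.** 15 − 4 = 11 minutes. One might ask whether 15 is the sum of several short tests. Three tests give 3 × 4 = 12 and five give 5 × 4 = 20, so neither matches. The same list gives COWS 5, pain 2 and craving 3 minutes, which read naturally as times per administration. I take 15 the same way.

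**Timing.** Data Management gives COWS five occasions (baseline, 1 h, 2 h, Day 2, Day 5). Pain and craving have those five plus Days 3 and 4, so 5 + 2 = 7. A test set at the same times as all three measures could therefore mean five or seven occasions, against the three listed for cognition. Days 3 and 4 may be done by phone, which does not suit a test described as in-office.

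**Practical size.** At the 1-hour visit, COWS, pain and craving take 5 + 2 + 3 = 10 minutes. With the Stroop the block takes 10 + 4 = 14 minutes; with the longer assessment, 10 + 15 = 25. The plan also sets the first buprenorphine dose one hour after placement, so staff need to know which test is meant. Over three occasions, testing takes 3 × 4 = 12 or 3 × 15 = 45 minutes per participant, a difference of 33.

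**What follows under each reading.**

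1. Design and Methods governs: executive function is measured, memory is not, and the memory part of the hypothesis has no data.
2. The efficacy list governs: several domain scores exist and memory may be among them, but the outcome for the MMRM is undefined.

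Neither reading gives a defined test of the memory hypothesis.

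**The case against.** The best defence is that only Design and Methods limits the test to executive function. The power section assigns memory to CNSVS, the efficacy list has domain scores in the plural, and Data Management and the analysis sections say CNSVS and never Stroop. The Stroop could be one component of a 15-minute assessment that also covers memory. The Aim 2 statement itself says only cognition; memory enters through the hypothesis.

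Much of this stands. A reader might infer from Design and Methods that the trial cannot answer half of its cognition aim. The documents do not support that, because the other sections point to a broader assessment. They do not confirm one either: no section lists the subtests, and no section names a memory score.

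The timing conflict is also the weaker part. The explicit list and the schedule table agree on three occasions, and the sentence in Design and Methods is general narrative. It still contradicts them and should be corrected.

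Two further inferences go too far. One is that sites would collect different data: this is a single-centre study, so the risk is one unclear instruction. The other is a numerical false-positive rate from choosing among scores: the documents give neither the number of domains nor their correlation, so no such figure can be supported.

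**Conclusion.** The inconsistency is real and limited in reach. Two descriptions of the cognitive assessment differ in content, in length (4 against 15 minutes) and in timing, and the memory hypothesis has no named outcome under either. Whether memory data will be collected cannot be settled from the documents.

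The conclusion rests on comparing the sections, with one assumption: that 15 minutes is the time for one administration. Cognition plays no part in the primary test or the sample size, and Sub-Group Analyses lists it apart from the primary and key secondary variables. The primary COWS result is unaffected. The point should be fixed because a wording change made before data collection protects part of a stated aim, and one made afterwards cannot.

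**What to change.** Reconcile Design and Methods, Data Management, the power section with its schedule table, and the efficacy list to one test, given at baseline, 1 hour and Day 5.

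- **If the 15-minute assessment is intended:** replace the Stroop wording in Design and Methods and list the subtests and domain scores. In Secondary efficacy analysis, name one memory score and one executive-function score as the MMRM cognitive outcomes, with one primary time point. The choice matters, because the 1-hour assessment is scheduled before the effect of the first buprenorphine dose and Day 5 after several days of treatment. Label any other domain score exploratory. Two comparisons remain, so the plan should also say how they will be interpreted together.
- **If only the Stroop is intended:** delete memory from the Aim 2 hypothesis and from the power section, and correct the efficacy list.

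Both options need only changes to protocol and SAP wording. The first also takes about 11 minutes more per test than Design and Methods implies, time that the efficacy list already budgets. The second costs nothing in clinic but gives up the memory question.
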